## 1.0 BACKGROUND AND RATIONALE

Glaucoma is a progressive optic neuropathy that causes characteristic loss of visual fields and can eventually lead to blindness. A major risk factor for glaucomatous visual field loss is elevated intraocular pressure (IOP; [The AGIS Investigators 2000](#)). The need for improved efficacy of glaucoma medications is supported by several clinical studies. Studies such as the Early Manifest Glaucoma Trial ([Heijl 2002](#)), the Ocular Hypertension Treatment Study ([Kass 2002; Kass 2010](#)), and the Collaborative Normal Tension Glaucoma Study Group ([Collaborative Normal-Tension Glaucoma Study Group 1998](#)) support the general conclusion that for delaying disease progression, every millimeter of reduction in IOP is significant. This conclusion holds true not only for ocular hypertensive and glaucoma patients with elevated IOPs but also for glaucoma patients with IOPs in the statistically normal range. Thus, the foundational goal for treating patients should be to lower the IOP, to the point that it prevents further damage to the optic nerve and achieve this without sacrificing safety or convenience.

Inhibitors of Rho kinase (ROCK) have emerged as a new class of IOP-lowering agents and recently, Rhopressa® (netarsudil ophthalmic solution) 0.02% was approved by the United States Food and Drug Administration for reducing elevated IOP. Three randomized and controlled clinical trials demonstrated up to 5 mmHg reductions in IOP for subjects treated with netarsudil 0.02% once daily (QD) in the evening. For subjects with baseline IOP <25 mmHg, the IOP reductions with netarsudil 0.02% dosed QD were similar to those with timolol 0.5% dosed twice daily ([Rhopressa® Prescribing Information 2017](#)).

Netarsudil 0.02% is a novel Rho kinase and norepinephrine transporter inhibitor developed at Aerie Pharmaceuticals, Inc. Netarsudil 0.02% lowers IOP through a distinct mechanism of action: increasing trabecular outflow by decreasing acto-myosin-driven cellular contraction and reducing production of extracellular matrix proteins ([Kazemi 2018; Lin 2018](#)). In preclinical studies, netarsudil 0.02% was shown to not only increase trabecular outflow facility ([Lin 2018; Wang 2015; Ren 2016; Li 2016](#)), but also to decrease episcleral venous pressure ([Kiel 2015](#)) and aqueous humor production ([Wang 2015](#)). The mechanisms of action of netarsudil 0.02% were further explored in a phase 1 study of healthy human volunteers, in whom netarsudil 0.02% QD was demonstrated to lower IOP primarily by increasing outflow facility, but also by reducing episcleral venous pressure ([Kazemi 2018](#)).

## 2.0 STUDY OBJECTIVE

The objective of this study is to evaluate the IOP lowering efficacy of netarsudil 0.02% when used as monotherapy or when used concomitantly with other IOP-lowering agents in subjects with elevated IOP due to open-angle glaucoma or ocular hypertension in a real-world clinical setting.

## 3.0 STUDY DESIGN

This is a multicenter, prospective, open-label study.

Subjects diagnosed with open-angle glaucoma or ocular hypertension will be evaluated at a Baseline Visit (Visit 1, Day 0). Subjects satisfying Visit 1 inclusion/exclusion criteria will be invited to participate in this study.

At the Baseline Visit (Visit 1, Day 0), all enrolled subjects will be dispensed netarsudil 0.02% and instructed to begin dosing in each eye QD in the evening. During the 12-week follow-up period, subjects will complete 2 visits (Visit 2: 6 weeks [ $\pm 7$  days], Visit 3: 12 weeks [ $\pm 7$  days]), during which IOP will be evaluated.

## 4.0 STUDY POPULATION

### 4.1 Number of Subjects

Approximately two hundred and fifty (250) male or female subjects will participate in this study.

## 4.2 Number of Study Centers

Approximately 32 study centers will be utilized in this study.

## 4.3 Subject Eligibility

To be eligible for enrollment into the study, subjects must meet all inclusion and exclusion criteria detailed in [Section 4.3.1](#) and [Section 4.3.2](#).

### 4.3.1 Inclusion Criteria

The following are criteria for inclusion in the study. Criteria required at the Baseline Visit (Visit 1, Day 0) ONLY are so indicated.

1. Male or female subjects (aged 18 or older)
2. Subjects diagnosed with open-angle glaucoma or ocular hypertension, and determined by the treating physician to require additional IOP-lowering treatment with netarsudil 0.02% either as first-line monotherapy, as a replacement of prior IOP-lowering medication, or used concomitantly with other IOP-lowering medication
3. Willingness to follow protocol requirements, including signed informed consent, routine follow-up schedule, completing questionnaires and completing laboratory tests

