### 4.3.2 Exclusion Criteria

The following are criteria for exclusion from the study:

1. Have any active ocular disease other than glaucoma or ocular hypertension that would interfere with study interpretation
2. Women of childbearing potential who are pregnant, nursing, or planning a pregnancy and not using a medically acceptable form of birth control. An adult woman is considered to be of childbearing potential unless she is 1 year post-menopausal or has a documented plasma follicle-stimulating hormone (FSH) level > 35 mIU/mL in conjunction with hormone replacement therapy or post-surgical sterilization (see [Section 7.4](#)). Male subjects with a female partner of childbearing potential must have had a prior vasectomy or agree to use an effective method of birth control during the treatment period and for 3 months after the subject has completed the study. All women of childbearing potential must have a negative pregnancy test result at the Baseline Visit and must not intend to become pregnant during the study
3. Known sensitivity or allergy to the study medication or components
4. Any systemic disease or clinical evidence of any condition which would make the subject, in the opinion of the investigator, unsuitable for the study or could potentially confound the study results
5. Concurrent participation or prior participation in any investigational drug or device study within the last 30 days prior to the Baseline Visit

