**5.1.4 Site Personnel Study Medication Instructions**

Subjects will be instructed to start self-administering study medication in each eye in the evening of the Baseline Visit (Visit 1) (see [Section 5.1.5](#) below). There is no washout period required for subjects replacing prior IOP-lowering therapy with netarsudil ophthalmic solution 0.02%.

Contact lens wear during the study is acceptable. However, subjects must remove their contact lenses before instillation of study medication and not place them in their eye(s) until 15 minutes after instillation.

If netarsudi 0.02% is to be used concomitantly with other topical ophthalmic drug products to lower IOP, each drug product should be administered at least 5 minutes apart to prevent washout.

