## 6.0 PRIOR AND CONCOMITANT THERAPIES

### 6.1 Allowed Medications or Treatments

Therapy considered necessary for a subject's welfare will be given at the discretion of the investigator and documented during the course of the study. The use of any concurrent medication (prescription or over-the-counter, including herbal medications) is to be recorded in a subject's source documentation (charts), as well as in the case report forms (CRFs), noting the date, dosage, frequency, start date, and reason for taking the medication(s).

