## **6 STATISTICAL METHODS**

All data processing, summarization, and analyses will be performed using SAS® Version 9.4 or higher.

Unless otherwise specified, for continuous variables, descriptive statistics will include the number of subjects/eyes (n), mean, standard deviation, median, minimum and maximum values. Categorical variables will be summarized using frequency and percentages.

Unless, otherwise stated, missing data will be handled as is, except when the aforementioned dates are required for calculations, the partial dates will have either '01' or 'Jan' imputed with an exception for dates related to AEs where the date closest to the last event (visit date, etc.) should be used rather than arbitrary '01' of that month.

All efficacy data will be summarized at each time point using appropriate descriptive statistics. Summaries will be presented for the ITT, mITT and PP populations. All summaries and analyses will be performed using data pooled across centers.

Baseline assessment will be those recorded prior to dosing. In cases where more than one pre-dose observation has been recorded, the **last recording** will be identified as the baseline assessment.

Study days will be numbered relative to the study starting date (Visit 1, presumably, the first dosing date).

Recorded data will be assigned to evaluation/assessment windows. If more than one clinical evaluation is made within a window for a particular visit, the record with the date closest to the targeted window will be used except for AEs where the **worst assessment** will be used.

Visit windows and analytical windows are defined as follow:

Visit	Targeted Window	Analytical Window
Visit 1 (Baseline, First dosing date)	Day 0	Day 0
Visit 2	Week 6 ( $\pm$ 7 day)	Day 2 to Day 63
Visit 3 (End of treatment visit)	Week 12 ( $\pm$ 7 days)	Day 64 to End of Study

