## 6.5 Efficacy Evaluation

Only **one** eye per subject will be included in the efficacy analysis.

If both eyes qualify for study inclusion, analyses will be provided for the worse eye at baseline. If both study eyes are the same at baseline, then data for only the right eye will be analyzed.

Efficacy analyses will be performed for the ITT, mITT and PP populations. Descriptive results will be presented for the overall group as well as for the Monotherapy and Concomitant Therapy groups.

[figure not shown]
There will be no statistical comparison between the Monotherapy and the Concomitant Therapy groups.

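### Nothing visible requires a concomitant IOP-lowering agent to be in use before Visit 1, so the effect of one started with netarsudil is counted as netarsudil's; a start-date sensitivity summary would show how much this matters

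*Protocol*

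**What the plan says.** The objective (Protocol 2.0, SAP 2) is netarsudil's IOP-lowering efficacy, alone or together with other IOP-lowering agents, in a real-world setting.

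- **Entry.** Criterion 2 in Protocol 4.3.1 leaves the route to the treating physician: first-line monotherapy, replacement of a prior drug, "or used concomitantly with other IOP-lowering medication". It sets no start date, minimum duration or unchanged regimen for the other drug.
- **Exclusions.** The nearest rule in Protocol 4.3.2 to one on confounding is "Any systemic disease or clinical evidence of any condition which would make the subject, in the opinion of the investigator, unsuitable for the study", extended to conditions that might confound the results. The only look-back on earlier treatment is "Concurrent participation or prior participation in any investigational drug or device study within the last 30 days prior to the Baseline Visit".
- **Other therapy.** Protocol 6.1: "Therapy considered necessary for a subject's welfare will be given at the discretion of the investigator and documented during the course of the study". The same section has the start date of each concurrent medication recorded.
- **Baseline and endpoint.** SAP 6: "Baseline assessment will be those recorded prior to dosing", taking the last reading if there are several. SAP 4.3 makes percent IOP reduction from that value the primary endpoint. SAP 3 describes a single-arm study.
- **Reporting.** SAP 6.5: "Descriptive results will be presented for the overall group as well as for the Monotherapy and Concomitant Therapy groups". No comparison between the two groups is planned. The only sensitivity analysis in SAP 6.5.3 uses the per-protocol population.

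**The concern.** Without a control arm, change from baseline estimates the effect of adding netarsudil to other therapy only if that therapy is already acting at baseline and then stays constant. The visible text does not secure the first condition. A subject who starts netarsudil and a second agent on the same day meets criterion 2 and enters both the Concomitant and the Overall summaries. That subject's reduction is the joint effect of two new drugs, while the objective attributes efficacy to one. A larger sample does not reduce the error, and no visible table would show it. At stake is whether the Concomitant result can be read as netarsudil's add-on effect or only as the change under the whole regimen.

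This is separate from drugs added during follow-up and from the replacement of a prior drug.

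**Working it through.** **No figure to reproduce.** SAP 3.3 says that no sample size calculation was performed. The only design number is about 250 subjects. All other figures below are assumptions, marked as such.

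**Step 1: does any visible rule cover the case?**

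| Place | What it covers | Covers an agent started at Visit 1? |
|---|---|---|
| Protocol 4.3.1, criterion 2 | Concomitant use | No timing condition |
| Protocol 4.3.2, exclusion 4 | Systemic disease or a condition, in the investigator's opinion | Does not name drugs |
| Protocol 4.3.2, exclusion 5 | Investigational studies, 30 days | No |
| Protocol 5.1.4, SAP 3.5 | No washout when a drug is replaced; no run-in described | No |
| Protocol 11.2, SAP 5.3 | Prohibited drugs and procedures during the study | None named in the visible text |

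**Step 2: how much is misattributed in one subject?** Let the other agent eventually lower IOP by E mmHg, with a fraction p of this already present in the baseline reading. The part falling after baseline is (1 − p) × E.

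- Started at Visit 1: p = 0, so all of E is counted as netarsudil's.
- Begun shortly before: p lies between 0 and 1, so only the remainder is counted.
- Fully established: p = 1, so nothing is counted.

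**Step 3: shift in a group mean.** Let f be the share of the group starting another agent at Visit 1, and d the percentage points that this agent adds to the subject's reduction. The shift is f × d. With f and d assumed:

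| f | d = 10 | d = 15 | d = 20 | d = 25 |
|---|---|---|---|---|
| 5% | 0.5 | 0.75 | 1.0 | 1.25 |
| 10% | 1.0 | 1.5 | 2.0 | 2.5 |
| 20% | 2.0 | 3.0 | 4.0 | 5.0 |

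Here f is the share of the group being summarised. If the Concomitant group were 125 of 250 (assumed), 20% of it is 25 subjects, or 25/250 = 10% of the Overall group. The largest shift of 5.0 points in the Concomitant mean would then be 10% × 25 = 2.5 points Overall.

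**Step 4: a worked case (assumed pressures).** An established add-on subject goes from 20 to 17 mmHg: 3/20 = 15.0%. A subject starting both agents goes from 26 to 17 mmHg: 9/26 = 34.6%. The excess is 34.6 − 15.0 = 19.6 points. The group mean with such subjects, against 15.0% without them, is:

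- 5%: 0.05 × 34.6 + 0.95 × 15.0 = 16.0%
- 10%: 0.10 × 34.6 + 0.90 × 15.0 = 17.0%
- 20%: 0.20 × 34.6 + 0.80 × 15.0 = 18.9%

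**Step 5: a yardstick.** The 95% half-width of a mean is 1.96 × SD/√n. With assumed SDs of 12, 15 and 20 points it is 1.5, 1.9 and 2.5 points at n = 250, and 2.1, 2.6 and 3.5 points at an assumed n = 125. A shift of 2.0 points (f = 10%, d = 20) is about the half-width at n = 250 and SD 15. At f = 5% the shift of 0.5 to 1.25 points is below every half-width listed.

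**The case against.** **Criterion 2 speaks of additional treatment, which suggests existing therapy.** This is the natural reading for many subjects, and starting two drugs together is not a named route. But the same phrase also covers first-line monotherapy, so it cannot require earlier therapy. Where earlier therapy exists, it need not be established.

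**Exclusion 4 already deals with confounding.** It concerns disease or a condition, at the investigator's discretion. It is not a rule on recently started drugs.

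**Group rules may exist where the reader cannot see them.** This stands as a limit. Figures in SAP 4.2 and 6.5 are not shown, the entry under SAP 6.3.4 on current IOP-lowering medications is blank, and part of Protocol 7.1.1 is redacted. The groups may already be defined from drugs current at baseline. The eligibility lists themselves show no redaction.

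**The study is real-world and descriptive.** Broad entry is a legitimate choice and need not change. It does not settle what the reduction may be attributed to.

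**A reader might infer more than the documents support.**

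- *That the whole drop from an agent begun just before Visit 1 goes to netarsudil.* Step 2 shows that only the part not yet present at baseline does.
- *That recent laser or surgery inflates the results, including Monotherapy.* The entry criteria set no interval since a procedure, but nothing in the documents establishes the direction or size of such an effect.
- *That the planned results are known to be inflated.* The documents permit the case but give no frequency for it.
- *That the Concomitant group should be redefined.* That would narrow a group named in Protocol 11.3.2, while SAP 1.1 declares no changes from protocol.

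**Conclusion.** The point holds in limited form. In the visible text, nothing requires a concomitant IOP-lowering agent to be in use before Visit 1, and no planned analysis separates the effect of one started with netarsudil. The misattribution is complete for a start at Visit 1 and partial for a start shortly before.

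Its size is unknown. The range of 0.5 to 5 percentage points rests on assumed shares of 5% to 20% and an assumed own effect of 10% to 25%. At the low end it is smaller than the sampling error of the mean; at the high end it would change how the Concomitant result is read. The conclusion also assumes that the content not shown holds no rule on this. Because the start dates that would reveal the frequency are already recorded, a sensitivity summary is a cheap and proportionate improvement.

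**What to change.** Keep the Overall, Monotherapy and Concomitant summaries, enrolment and care as planned. Then:

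1. In SAP 6.5.3, pre-specify a sensitivity summary of the primary endpoint, Overall and Concomitant. It excludes subjects with any other IOP-lowering agent started at Visit 1 or within a stated interval before it, based on recorded medication start dates. Report the number excluded from each group. The sponsor chooses and justifies the interval before database lock.
2. State how partial start dates enter this rule. SAP 6 fills a missing day with 01 and a missing month with Jan where a date is needed for a calculation. Within the known month or year this can only move a start earlier or leave it unchanged, so a recent start may look established. One option is to show the summary twice, treating undetermined dates first as recent and then as established.
3. Extend the exclusion to recent IOP-affecting procedures only if their dates are recorded. SAP 6.3.2 summarises prior ocular procedures, but no visible text says that their dates are collected.
4. If the two summaries differ, describe the main Concomitant result as the change under the whole regimen.
5. If the content not shown already defines the groups by baseline medication, state that rule in the text of SAP 6.5.

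The cost is SAP wording and one extra table set, a slightly smaller sensitivity sample, and an interval that must be fixed in advance.

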### 4.3.2 Exclusion Criteria

The following are criteria for exclusion from the study:

1. Have any active ocular disease other than glaucoma or ocular hypertension that would interfere with study interpretation
2. Women of childbearing potential who are pregnant, nursing, or planning a pregnancy and not using a medically acceptable form of birth control. An adult woman is considered to be of childbearing potential unless she is 1 year post-menopausal or has a documented plasma follicle-stimulating hormone (FSH) level > 35 mIU/mL in conjunction with hormone replacement therapy or post-surgical sterilization (see [Section 7.4](#)). Male subjects with a female partner of childbearing potential must have had a prior vasectomy or agree to use an effective method of birth control during the treatment period and for 3 months after the subject has completed the study. All women of childbearing potential must have a negative pregnancy test result at the Baseline Visit and must not intend to become pregnant during the study
3. Known sensitivity or allergy to the study medication or components
4. Any systemic disease or clinical evidence of any condition which would make the subject, in the opinion of the investigator, unsuitable for the study or could potentially confound the study results
5. Concurrent participation or prior participation in any investigational drug or device study within the last 30 days prior to the Baseline Visit

### 4.3.3 Subject Withdrawal Criteria

Criteria and procedures for handling subjects who are discontinued from the study are described in [Section 9.2](#). Subjects who are discontinued will not be replaced.

## 5.0 STUDY MEDICATION AND OTHER STUDY SUPPLY INFORMATION

### 5.1 Study Medications

#### 5.1.1 Study Medication Information

Enrolled subjects will be instructed to self-instill 1 drop of netarsudil 0.02% in each eye QD in the evening, beginning the evening of the Baseline Visit (Visit 1).

Netarsudil ophthalmic solution 0.02% will be provided by Aerie Pharmaceuticals, Inc. in the marketed containers and available for dispensing at the Baseline Visit (Visit 1, Day 0) and Visit 2 (Week 6).

Detailed information is provided in the Rhopressa Package Insert ([Appendix 3](#)).

#### 5.1.2 Formulations

Netarsudil 0.02%

Name: Rhopressa® (netarsudil ophthalmic solution) 0.02%  
Active ingredient: netarsudil mesylate 0.285 mg  
Other ingredients: mannitol, boric acid, sodium hydroxide to adjust pH and water for injection, benzalkonium chloride 0.15 mg (preservative)

#### 5.1.3 Storage, Handling, Dispensing and Reconciliation of Study Medications

The study medication must be stored refrigerated at 2° to 8°C (36° to 46°F) at the study site in a secure area and administered only to subjects entered into the clinical study, at no cost to the subject, in accordance with the conditions specified in the protocol.

Store netarsudil 0.02% at 2° to 8°C (36° to 46°F) until opened. After opening, the product may be kept at 2° to 25°C (36° to 77°F) for up to 6 weeks.

Subjects are to save all used/unused bottles for presentation to designated study staff during office visits.

##### **Study Medication Supply Records at Study Sites:**

It is the responsibility of the investigator to ensure that a current record of study medication disposition is maintained. Records or logs should include:

- Amount received and placed in storage area
- Dates and initials of the person(s) responsible for each product inventory entry/movement
- Amount dispensed to and returned by each subject, including unique subject identifiers
- Amount transferred to another area for dispensing or storage if necessary
- Non-study disposition (eg, lost, wasted, broken)

##### **Destruction of Study Medication Supplies:**

After subjects have completed study medication usage, all study medications (used and unused) will be collected by a designated staff. Only upon direction of sponsor and after reconciliation, all used/unused or undispensed study medication will be destroyed at the study site according to the site's usual medication destruction practices.

**5.1.4 Site Personnel Study Medication Instructions**

Subjects will be instructed to start self-administering study medication in each eye in the evening of the Baseline Visit (Visit 1) (see [Section 5.1.5](#) below). There is no washout period required for subjects replacing prior IOP-lowering therapy with netarsudil ophthalmic solution 0.02%.

Contact lens wear during the study is acceptable. However, subjects must remove their contact lenses before instillation of study medication and not place them in their eye(s) until 15 minutes after instillation.

If netarsudi 0.02% is to be used concomitantly with other topical ophthalmic drug products to lower IOP, each drug product should be administered at least 5 minutes apart to prevent washout.

